2.0 BACKGROUND and SIGNIFICANCE

Vulvar lichen sclerosis (LS) is a well-characterized dermatosis resulting in labial atrophy, synechiae and introital narrowing and can often cause dyspareunia, itching and co-existent vulvar pain. Biopsy is necessary to confirm the clinical diagnosis and the mainstay of treatment usually consists of topical steroid therapy.¹

Clobetasol propionate and mometasone furoate are potent topical steroids that have long been considered gold-standard treatment for vulvar lichen sclerosis and work through anti-inflammatory, anti-mitotic, and immunosuppressive effects. One of the complications of long-term steroid use, however, is potential thinning of the vulvar skin, therefore limiting long-term use. Other therapeutic options include topical calcineurin inhibitors, surgery including incision and skin graft treatment, cryotherapy and phototherapy. Table 1 summarizes current clinical comparative trials for lichen sclerosis involving topical steroid therapy. Clobetasol propionate has a range of efficacy from 61-91% depending on the selected outcome criteria.

Table 1.

Author/year	Study Design	N	Outcome	Results
Bracco, GL 1993 ²	RCT Clobetasol vs. testosterone vs. progesterone vs. cream based therapy	79	-Subjective scaled symptom remission of vulval LS -Objective histologic and gross improvement	-75% remission with Temovate versus 10% Progesterone, 20%Testosterone, and 10% cream based treatments had subjective remission of LS -Only Clobetasol propionate had significant histologic and gross improvement.
Terra S, 2014 ³	RCT clobetasol vs. phototherapy	15	-Mean relative reduction of total clinician's score (TCS): subjective pruritus and burning/pain VAS, Skindex-2, 20 MHz- ultrasonography, histopathological analysis	35.6% decrease in mean (total clinical score) TCS in UV-A1 phototherapy group -51.4% decrease in mean TCS for clobetasol propionate group; Skindex-29, pruritus, burning/pain significantly decreased -Phototherapy group's only significant difference was with burning/pain -Significant difference in dermal density on ultrasound and histopathological reduction of

				inflammatory infiltrate in clobetasol propionate group and not Phototherapy group
Lorenz B, 1998 ⁴	Retrospective	81	-Subjective patient improvement of symptoms (pruritus, irritation, burning and dyspareunia) -Subjective clinician improvement of appearance	-77% complete remission symptoms, 18% partial remission, and 5% no change after treatment with clobetasol propionate -32% of patients had subjective complete remission of symptoms and 46% patients with subjective partial remission of symptoms
Funaro D, 2014 ⁵	RCT Clobetasol vs. tacrolimus	55	-Subject visual analog scale of symptoms (burning/pain, pruritus, and scaled improvement of condition) -Clinician cutaneous exam and photographs	-Clobetasol propionate had 66% efficacy of complete removal of subjective clinical signs compared to 14% in the tacrolimus group. -Objective clinical exam revealed clobetasol propionate group had more significant decreases in vulvar skin papules and atrophic patches than tacrolimus group.
Virgill A, 2014 ⁶	RCT clobetasol vs. mometasone	48	-Subjective (visual analog scale and gynecologic subjective scale) -Objective (four point scale and gynecologic objective scale) scores improvement by 75%	-59% of clobetasol group and 37% of mometasone furoate group had subjective score improvement. -67% of clobetasol and 48% of furoate group had objective score improvement
Ayhan A, 2007 ⁷	Retrospective	140	Subjective clinical response in six months	91.7% of clobetasol group and 77.5% of testosterone group reported subjective improvement

The vulvovaginal SmartXide⁸ –V2-LR laser system by DEKA (Calezano, Italy) is a fractional CO₂ laser with maximum 40 Watt power and laser energy emission at 10,600 nanometer wavelength which is mainly absorbed by water in the underlying tissue. The SmartXide⁸–V2-LR system was first introduced in 2009 with DOT therapy distributing fractioned CO₂ laser in small spots of 200 microns to the vulvar skin or vaginal epithelium, resulting in a portion of the skin remaining intact with less tissue destruction and faster healing. The device is cleared by the US Food and Drug Administration (FDA) for incision, excision, ablation, and coagulation of gynecologic soft tissues. The fractioned therapy has been shown to stimulate fibroblastic growth through activation and biosynthesis of collagen and restoration of the extracellular matrix with collagen fibers.

D-Pulse DOT therapy involves two types of energy:

- 1) An initial high energy peak that allows laser energy removal of the superficial epithelial component
- 2) A second variable lower peak power that enables the laser energy to penetrate into the submucosa stimulating new collagen synthesis

The histopathologic changes associated with the CO₂ laser treatment are supportive for reconstituting the vaginal epithelium back to physiologic function in patients with severe vaginal atrophy. The atrophic vaginal epithelium in GSM is thin with few cycles having glycogen storage rendering the vaginal pH less acidic and the epithelium completely atrophic. Two months after treatment, the epithelium is thickened with proliferating basal cells beneath. The structural integrity of the epithelium is enhanced with newly formed papillae and capillaries supporting the vaginal ecosystem. Epithelial cells have remarkably more glycogen forming the characteristic superficial, intermediate and deep layers. Fibroblasts undergo protein production to create the extracellular matrix including collagen.⁹ The mechanism by which the carbon dioxide laser is hypothesized to work is by thermal energy creating heat shock of proteins. As a result of the damage, cytokines and growth factors are released signally molecules to recruit fibroblasts and increase cell division.¹⁰ Table 2 includes prior

studies involving CO2 laser treatment for lichen sclerosus in both men and women. Studies are all retrospective and small in number with limited follow-up and only subjective outcome criteria.

Table 2. Prior studies using Fractional CO2 laser for lichen sclerosus

Author and year	Trial Design	Primary Outcomes	Findings	Complications
Peterson C, 2004 ¹¹	Case Report	Subjective symptoms Visual re-epithelization	All patients(N=2) with refractory anogenital lichen sclerosus had resolution of symptoms and re-epithelization after 2-3 years with CO2 laser therapy	None
Kartamaa M, 1997 ¹²	Case Series	Subjective assessment of lichen sclerosus (better, asymptomatic, some recurrence)	Among male and female patients (N=10) with biopsy proven refractory LS, 76% were asymptomatic after CO2 laser treatment with mean follow up of 32 months.	Three patients needed repeat treatment
Windahl T, 2006 ¹³	Retrospective cohort	Subjective patient assessment of recurrence of symptoms, any visible penile lesion, recurrence of meatal stenosis	In men with histologically verified penile lichen sclerosus treated with CO2 laser, 80% (N=50) had no local symptoms at mean follow up 14 years	Two patients required further treatment
Lee A, 2015 ¹⁴	Case Series	Subjective symptom resolution	In women (N=5) with biopsy confirmed severe vulvar LS recalcitrant to topical corticosteroid treatment; four of whom responded positively to fractional CO2 laser treatment, and one to ablative CO2 laser therapy	Two patients needed repeat treatment at 6-8 months Two patients reported discomfort with laser treatment
Ratz L, 1984 ¹⁵	Case Report	Subjective symptom resolution and re-epithelization	One case of balanitis xerotica obliterans refractory to topical treatments resolved after CO2 laser treatment	Syncopal episode after treatment

Very little is known about long-term effects of CO2 fractional laser therapy use in the vulva or vagina, although the treatment is widely accepted in plastic and cosmetic surgery and dermatology. Increased marketing for laser vaginal rejuvenation has spawned a proprietary female genital cosmetic surgery industry in the US with very limited published outcome data. SmartXide⁸ –V2-LR has some established outcome data for treatment of genitourinary syndrome of menopause GSM, also known as vulvovaginal atrophy. Table 3 List outcomes of the SmartXide⁸ –V2-LR system for treatment of vaginal atrophy.

Table 3 Outcomes of SmartXide⁸ –V2-LR system for Vaginal Atrophy

Author and year	Trial Design	N	Primary Outcomes	Findings	Complications
Salvatore R, 2014 ⁸	Prospective	50	Objective vulvovaginal atrophy (VVA) symptoms- Vaginal Health Score Index (VHIS) Subjective VVA symptoms – 10 point visual analog scale	Fractional CO2 laser improved VVA all subjective symptoms in women; significant objective improvement VHIS (13.1+/- 2.5 at baseline vs. 23.1 +/- 1.9; p<0.001)	None

			(burning, vaginal itching, vaginal dryness, dyspareunia, and dysuria)		
SalvatoreR, 2015 ¹⁶	Prospective	77	-Sexual function and quality of life (Female sexual function index and Short form 12) -Subjective symptoms (vaginal burning, dryness, dyspareunia, and dysuria with visual analog scale)	-85% normal sexual life after CO2 laser therapy in not sexually active group -Significant improvement in FSFI and VAS scores after treatment -Significant improvement in overall satisfaction with sexual life after laser treatment	None

3.0 STUDY DESIGN

Women presenting to the urogynecology clinic will be screened for lichen sclerosus. Vulvar biopsy will be performed for confirmation, and, if eligible, the patient will be consented to undergo baseline questionnaires, photodocumentation of vulvar lesions and randomization. Patient will be randomized to monthly LASER treatment for 3 months or topical STEROID therapy (temovate propionate .05% ointment nightly for one month, three times weekly for 2 additional months, then as needed) in a 1:1 ratio using a computer generated randomization schedule. Grouping assignments will be kept in sealed consecutively numbered, opaque envelopes. Because of the nature of the treatment, it will not be possible to blind patients but the assessor will be blinded to the intervention.

Patient questionnaires include multiple validated scales and surveys to provided reproducible measures of vulvar symptoms as primary and secondary outcomes. Questionnaires will be completed at the intake visit, repeated at 12 weeks after treatment is completed or 6 months from intake, and one year follow up. Subjective symptoms including vulvar itching, vulvar burning, vulvar irritation, pain with intercourse, tearing of the vulvar skin, painful urination, and painful defecation will be rated with a validated visual analog scale (VAS), scaled 0-10, see appendix 1. Higher values correspond to more bothersome symptoms. The Skindex-29 questionnaire is a subjective measure of skin symptoms validated against the Medical Outcomes Study 36-item Short-Form Survey (SF-36)¹⁷, appendix 2. The Skindex-29 was developed in dermatology and modified for use in vulvadynia¹⁸. The Skindex-29 is scored as a sum expressed on a 100-point scale with higher scores indicating lower quality of life. Validated quartiles are used to characterize disease symptoms, emotions, functioning, and overall score as either very little, mild, moderate, or severe¹⁹. Secondary outcomes of patient satisfaction and global impression of improvement will be collected using simple validated visual analog scale from 0-5, much worse to much better, appendix 4. A final subjective measure, the Vulvovaginal Symptoms Questionnaire (VSQ), a validated measure of vulvar symptoms, emotions, life impact, and sexual impact in postmenopausal women will be collected a secondary outcome²⁰, appendix 5. A higher total score on the VSQ corresponds to lower quality of life.

Objective measures of the clinical appearance of vulvar lichen sclerosus will be completed by investigators at concurrent time points with the patient questionnaires. Non identifiable photo documentation of vulvar appearance will be completed using Fujifilm JX665 Digital Camera. Investigators blinded to treatment arm will complete visual assessment including white plaques/hypopigmentation, cigarette paper/thin skin, introital narrowing, perianal involvement (figure of eight shape), loss of labia minor, fusion of labia minora, phimosis of clitoral hood, vulvar fissure, and erosion scaled on validated visual analog scale, rated 0-10 from absent to severe, see appendix 1. Lower objective VAS scores corresponds to less severe Lichen Sclerosus disease. In addition, investigators will complete validated Vaginal Health Index (VHI) at all time points²¹, appendix 3. The VHI evaluates vulvovaginal overall elasticity, fluid secretion type and consistency, pH, epithelial mucosa, and moisture on a scale 1-5 from none to excellent. A lower VHI score corresponds to greater urogenital atrophy.

The laser used in this clinical investigation complies with federal laser performance standards.

Fractional CO2 laser with 10600 um wavelength, 60 W pulse, continuous or pulsed with repetition rate, articulated arm with scanner hand-piece, 120 Vac power and 635 nm aiming beam. The laser power will be set at 26 W, dwell time of 800 microseconds, DOT spacing at 800 micro meters and normal scan mode. Vulvar lichen sclerosis will be treated except for the clitoris glans and clitoral hood which will be spared with at least 5mm margin. The procedure will be performed in the outpatient clinic at the National Center for Advanced Pelvic Surgery at MedStar Washington Hospital Center or Medstar Lafayette Center, and include 3 sessions, 4 weeks apart. A minimum of 2 weeks are required from the time of biopsy to treatment. Prior to treatment eutectic local anesthetic (EMLA) will be applied for at least 5 minutes up to 30 minutes and then wiped off prior to laser treatment. Photodocumentation will take place at baseline and at 6 months and one year following the last LASER or STEROID treatment. Interpretation of photodocumentation with clinical objective scale will be completed by blinded provider.

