5.0 SAMPLE SIZE CALCULATION

The study will consist of 2 study groups (LASER vs STEROID therapy). We expect improved subjective and objective results in the LASER group at 3 months post treatment or 6 months from enrollment compared with the STEROID group.

This study is designed as a two-group randomized clinical trial. Sample size calculations were conducted using the absolute change in the Skindex 29 as the primary end point. Our study will reach 80% power to detect a mean difference of 16 points on the Skindex 29 (sd=22 for both groups)²² between the study groups with 24 patients in each group, or 48 in total based on a one-sided two-sample t-test with alpha=0.05. By accounting for 10% attrition, we propose to recruit 52 patients to the study to be randomized with a 1:1 ratio to each group, with a blocked component for those who used topical clobetasol in the past. The Skindex-29 has validated cutoff categories for mildly, moderately, and severely impaired health related quality of life scores, the mean difference between each quality of life measure overall score is between 6 and 7. Therefore, powering the study for a detection of mean difference of 16 points should measure significant quality of life improvement.^{23,24}

Study Timeline:

	Intake Visit	Day 0	2 weeks	4 weeks-14 weeks	6 months	1 year
Vulvar biopsy (if never completed)	X					
Vaginal STEROID or LASER			STEROID daily x 4 weeks LASER monthly x 3 months	STEROID three times weekly x 8 more weeks, then as needed LASER STOP at 12 weeks		
Vaginal Health Index scale (VHIS)		X			X	x
SkIndex-29 Vulvar QoL Questionnaire Vulvovaginal Symptoms Questionnaire (VSQ)		X			X	x
Telephone call to check compliance and answer questions			X	X (8 weeks)		
Photodocumentation		X			X	x
Questionnaire of patient global impression of improvement and satisfaction PGI-I					X	x

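### Photographs are timed from the last treatment, against the common 6-month and 1-year visits given elsewhere, and the six-week complication time has no origin or matching assessment

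*Combined protocol and SAP*

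**What the plan says.** **Photographs.** Section 3.0 states: "Photodocumentation will take place at baseline and at 6 months and one year following the last LASER or STEROID treatment". It adds: "Interpretation of photodocumentation with clinical objective scale will be completed by blinded provider". Section 1.0 names photographs for the secondary outcome of objective cure at 6 months and 1 year, without an origin.

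**Other timing statements.** Earlier in section 3.0, objective measures "will be completed by investigators at concurrent time points with the patient questionnaires". Questionnaires are "repeated at 12 weeks after treatment is completed or 6 months from intake, and one year follow up". The timeline in section 5.0 marks photographs in the same Day 0, 6-month and 1-year columns as the questionnaires, for both arms. Section 6.0 lists in-person visits at baseline, 6 months and 1 year. Section 11.0 ends recruitment in August 2018 and one-year follow-up in August 2019.

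**Treatment.** Section 3.0 gives laser as "3 sessions, 4 weeks apart". The timeline has "LASER STOP at 12 weeks" and, for steroid after the first four weeks, "STEROID three times weekly x 8 more weeks, then as needed".

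**Complications.** Section 1.0 lists them at 6 weeks, 6 months and 1 year, with no origin for the first. Before 6 months, the only scheduled contacts common to both arms are telephone calls at 2 weeks and 8 weeks (2 months in section 6.0), which the timeline describes as being for compliance and questions. The timeline has no row for complications. Section 8.0 promises adverse-event monitoring of all participants, without time points.

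**The concern.** The photograph sentence uses a different clock from the rest of the plan. The last treatment falls at different weeks in the two arms, and steroid continues as needed after its fixed course, so whether that use counts as treatment decides whether the steroid arm has a fixed photograph date. Patients cannot be blinded (section 3.0), which makes the blinded photograph reading a valuable safeguard. If its timing depended on arm, part of any difference could come from timing.

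For complications, an assessment time that matches no assessment leaves early events to be picked up as they happen to be mentioned. Laser patients are seen in person at their sessions and steroid patients are not, so the same event may be more likely to be recorded in one arm. The trial's stated purpose includes comparing safety.

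**Working it through.** **Inputs and assumptions.** Six months = 26 weeks, 1 year = 52 weeks, visits counted from Day 0. Treatment starts at week S = 0 or S = 2; the timeline first shows treatment in its 2-week column. Laser sessions fall at S, S+4 and S+8 (section 3.0). The fixed steroid course is 4 + 8 = 12 weeks and ends at S+12 (section 5.0). The 12-week laser stop may be a limit or the last session; if it is the last session, that falls at week 12 from Day 0 or at S+12, so week 12 or 14.

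**The plan's own pairing.** Section 5.0 sets the main comparison "at 3 months post treatment or 6 months from enrollment". For steroid, end of fixed course plus 12 weeks is 24 or 26, against 26. For laser it is 20 or 22, or 24 to 26 if the stop is the last session. The two halves roughly agree only if treatment is taken to end at about 3 months.

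**Photographs if the section 3.0 sentence is followed** (last treatment + 26 and + 52):

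| Reading | Last treatment, week | 6-month photograph | One-year photograph | Weeks after the visit at 26 or 52 |
|---|---|---|---|---|
| Laser, three sessions | 8 or 10 | 34 or 36 | 60 or 62 | 8 or 10 |
| Laser, last session at the 12-week stop | 12 or 14 | 38 or 40 | 64 or 66 | 12 or 14 |
| Steroid, fixed course | 12 or 14 | 38 or 40 | 64 or 66 | 12 or 14 |

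Gap between arms: 12 - 8 = 14 - 10 = 4 weeks under the three-session schedule; 0 to 2 weeks if the stop is the last session (12 against 12, 12 against 14, or 14 against 14).

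**If as-needed use counts.** A patient still using steroid at week 26 has her first follow-up photograph no earlier than 26 + 26 = week 52. That is 52 - 40 = 12 to 52 - 34 = 18 weeks after the laser arm, with no fixed date.

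**End date.** A patient enrolled in August 2018 would have her one-year photograph 8 to 14 weeks beyond 52 weeks, so after August 2019. Section 11.0 also describes August 2015 to August 2018 as 5 years, although it is 3; August 2018 is used here because the August 2019 end matches it.

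**Six weeks for complications.** From Day 0: week 6. From treatment start (S+6): week 6 or 8. From end of treatment: laser 14 or 16 (18 to 20 if the stop is the last session), steroid 18 or 20. Common contacts are at weeks 2, 8, 26 and 52. Only week 8, counted from a week-2 start, coincides with one, and complications are not part of that call's stated purpose.

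**In-person contact after Day 0 and before 6 months.** Laser: sessions at 0, 4, 8 give 2; sessions at 2, 6, 10 give 3. Steroid: none scheduled.

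**Sample size.** The 24 per group reproduces (difference 16, SD 22, one-sided alpha 0.05: n = 24.08 by t-test, power 79.9% at 24) and does not depend on any of this.

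**The case against.** The strongest reply is that the plan is clear enough in practice. Section 1.0's time frames, the concurrent-time-points sentence, the timeline and the visit list all suggest common visits, and staff would probably follow the timeline. The paired anchors in sections 3.0 and 5.0 imply that treatment ends at about 3 months, so as-needed use is probably not what the photographs are counted from. One could also read the sentence so that only the one-year photograph is counted from the last treatment.

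Much of this stands. A reader might infer that the steroid photographs have no date at all. The documents do not support that: it holds only if as-needed use counts as treatment, which the paired anchors suggest it does not, although the photograph sentence itself does not say. A reader might also infer that the arms will be photographed at different times. That too goes beyond the text, since most passages point the other way.

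What remains is that the fixed-course reading supplies a date without removing the conflict, because photographs would still come 8 to 14 weeks after the visits. The narrower grammatical reading repairs only the 6-month photograph and leaves the one-year one late.

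On complications, it is fair to answer that section 8.0 promises close monitoring, so it would be wrong to say that early events go unmonitored. But that section gives no time points and no list common to both arms, so it neither anchors the six-week assessment nor evens out the contacts.

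**Conclusion.** The point holds as a conflicting sentence that should be corrected, plus an outcome time that needs an origin and a contact. Followed as written, with treatment ending at the fixed course, the photograph rule gives about weeks 34-40 and 60-66 instead of 26 and 52. Laser would be 8-10 weeks late under the three-session schedule (up to 14 if the 12-week stop is the last session), steroid 12-14 weeks late, and the arms up to 4 weeks apart. These figures rest on the assumed start at week 0 or 2 and on courses kept to schedule.

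The reach is limited to the blinded photograph reading for secondary objective cure. The documents do not say whether the signs scale is scored from examination, photographs or both, so nothing is concluded about that scale as a whole. A reader might extend the problem to the main result; the powered Skindex-29 endpoint does not use photographs, so that does not follow. Its own either-or timing needs the same single origin.

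For complications, unequal recording is a risk rather than a demonstrated bias: 2-3 in-person laser sessions against no scheduled in-person steroid visit between Day 0 and 6 months, with no common list.

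**What to change.** **Photographs and visit times.**
- In section 3.0, drop the count from last treatment. State that photographs are taken at the common 6-month and 1-year visits in both arms, at the same visit as the questionnaires.
- Count those visits from one stated origin. Intake, enrollment and Day 0 are all used now and must be reconciled. Use that origin in place of the either-or wording in sections 1.0, 3.0 and 5.0.
- Reconcile the 12-week laser stop in section 5.0 with the session schedule in section 3.0. Which applies is for the sponsor to state.

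**Complications.**
- Ask the same section 1.0 complication list in both arms at the existing 8-week call and at the 6-month and 1-year visits, worded as since the last contact and with an onset date.
- Restate the six-week time in section 1.0 to match. If the sponsor meant six weeks after treatment, a new contact would be needed instead.
- Keep all events, including those noted at laser sessions, in the main safety report.

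**Cost.** Wording and a slightly longer call; no extra visits and no change in sample size. There are two limits. The 8-week call falls at or before the third laser session (week 8 or 10), so later events rest on unprompted reports or on recall at 6 months: 26 - 10 = 16 to 26 - 8 = 18 weeks later, or 12 to 14 if the last session is at week 12-14. And a common calendar origin equalises calendar time, not time off treatment.
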